14.1 Ethical approval

Ethics Committee (EC) approval and SSI approval (where required) will be sought through the Integrated Research Application System (IRAS) process. Any substantial changes to the Trial will be sent to the EC for approval and nonsubstantial sent as notification only. All SAEs that are unexpected and related will be sent to the EC within the appropriate time lines.

The main observational study of Stage 1 raises the following ethical considerations and arrangements:

1) Participants will have provided written informed consent/assent at the outset of the study, before they are prescribed an antibiotic. With their consent, all service users will have a representative identified, to either be approached to provide consent on their behalf or to be notified that the service user is taking part in the study. Consent will be checked at the time of a decision by the GP to prescribe antibiotics for the service user. 2) A central infection control advice centre for all Trial care homes will be selected to deal with the issue of the potential increase in identified *C. difficile* infection.

3) All care home staff will be trained in reporting SAEs and upon receiving an SAE the Chief Investigator (or nominated delegate) will asses the SAE for seriousness, causality and expectedness to determine whether expedited reporting needs to happen.

4) Participants will have the right to withdraw from the trial at any time, without their care being affected.

Sub-Study Considerations:

The prevalence sub-study of *C. difficile* asymptomatic carriage is an optional element to the main observational study. Service users will be able to participate in the observational study of Stage 1 even if they do not wish to enter this sub-study.

For the Qualitative Observational Study of Care Home Routines, Care home staff will be informed that a researcher is observing daily care routines. Service users and relatives will not be informed that a researcher is observing daily care routines. This is being conducted as a pre-research study (ie. to inform the design of PAAD stage 2) and not a research study. Therefore consent from care home staff or the service users and their relatives will not be sought.

Consent for the qualitative study will be sought from participants capable of giving consent. It is expected that this sub-study will commence at approximately 5 months after the recruitment start for the main observational study.

For the EQ-5D by Proxy study, the Care Home manager will be approached to give permission for the Care Home to take part in this sub study and for all Care Home Carers and residents to be approached about the sub study. The existing PAAD agreement will be amended to reflect their participation in the EQ5D Sub Study.

All assigned carers in each recruited home will be approached by the researcher, issued with an information sheet about the study, and asked to consent to take part. They will then be asked to identify all service users (SUs) they are assigned to. For each SU, the carer will be asked how long they have been their assigned carer, and if they consider each of their SUs to have general difficulties in their cognitive ability (i.e. competent or non-competent). The carer may ask the researcher any questions they wish about the study.

Each SU will be approached by the researcher, provided with an information sheet about the study, and asked to provide their consent to participate. Again, the SUs can ask any questions they have about the study and may discuss this with their carer, family and friends if they wish. If they do not wish to participate in the study, this will not affect the care they receive in any way. If they would like to participate but are unable to complete questionnaires due to physical difficulties, the researcher can help them by reading the questions and by noting their own responses if required. If they are unable to provide the researcher with consent due to cognitive difficulties, assent will be sought from their assigned consultee.

In this case, the consultee will be provided with an information sheet and asked to provide assent for their SUs participation in the study. If they are agreeable, the SU will be entered into the study.

In the event that SU cannot provide informed consent, when available, the most frequently visiting relative or friend of the consented/assented SU (known as **relative**) will be approached by the researcher, provided with an information sheet, and asked to provide their consent to participate in the study. If they wish to participate, it will then be possible to gather triad data for this SU (i.e. from SU, carer and relative). If the relative does not wish to participate, it will only be possible to gather diad data for this SU (i.e. from SU and carer).

The relative will also be asked to provide details on the nature of their relationship to the SU (e.g. sister, brother, daughter, son, grandchild, friend, etc) and the frequency of their visits (e.g. number of days weekly/monthly/annually.

Participants will have the right to withdraw from the any part of Sub-studies at any time, without their care being affected.

14.2 Data Handling

Electronic data will be stored on fire walled University computers. Files will be password protected and only accessible to researchers responsible for the running of the study and the Chief Investigator. All procedures for data storage, processing and management will be in compliance will the Data Protection Act 1998. All paper records will be stored in a locked filing cabinet, with keys available only to researchers and the chief investigator. The Trial Statistician will carry out analysis. All essential documents generated by the trial will be kept in the Trial Master File.

14.3 Confidentiality

The care home study staff will ensure that the service users' anonymity is maintained. The service user will be identified only by initials, date of birth and a service user ID number on the CRF and any electronic database. All documents will be stored securely and only accessible by trial staff and authorised personnel. The study will comply with the Data Protection Act which requires data to be anonymised as soon as it is practical to do so.

14.4 Indemnity

Cardiff University will provide indemnity and compensation in the event of a claim by, or on behalf of participants, for negligent harm as a result of the study design and/or in respect of the protocol authors/research team. Cardiff University does not provide compensation for non-negligent harm.

14.5 Trial sponsorship

Cardiff University will act as sponsor for trial. Delegated responsibilities will be assigned to the Care Homes taking part in this study.

14.6 Funding

This Study is funded by the NIHR HTA.

15 Data monitoring & quality assurance

Direct access will be granted to authorised representatives from the sponsor, host institution and the regulatory authorities to permit trial-related monitoring, audits and inspections.

The study will be conducted in accordance with the current approved protocol, ICH GCP, relevant regulations and standard operating procedures.

15.1 TSC (Trial Steering Committee)

The TSC will consist of an independent chair, two/three other independent members. The appropriate disciplines will be covered within the TSC members. The Chief Investigator, trial manager and statistician will attend as observers. The TSC will provide overall supervision for the trial and provide advice through its independent chair. The ultimate decision for the continuation of the trial lies with the TSC.

15.2 IDMC (Independent Data Monitoring Committee)

The IDMC will consist of an independent chair and two/three other independent members. We will ensure that all appropriate disciplines are covered in choosing the IDMC members. The first meeting will be before the main RCT commences to review the protocol and agree on timelines for interim analyses to take place. The main role of the IDMC is to review the data periodically and make recommendations to the TSC.

15.3 TMG (Trial Management Group)

The TMG will consist of the Chief Investigator, co-applicants and collaborators, Trial Manager, Trial Statistician and Trial Secretary. The role of the TMG is to help set up the study by providing specialist advice, input in and comment on the study procedures and documents (PIS, protocol etc) and advise on the promotion and the running of the trial. The group will meet monthly during the study. This group will also review and advise on the reporting of SAEs.

16 Publication policy

All publications and presentations relating to the study will be authorised by the Trial Management Group. The first publication of the trial results will be in the name of the Trial Management Group, if this does not conflict with the journal's policy. If there are named authors, these will include at least the trial's Chief Investigator, Statistician and Trial Coordinator. Members of the TMG and the Data Monitoring Committee will be listed and contributors will be cited by name if published in a journal where this does not conflict with the journal's policy. Authorship of parallel studies initiated outside of the Trial Management Group will be according to the individuals involved in the project but must acknowledge the contribution of the Trial Management Group and the Study Coordination Centre.

17 PAAD Sub Studies

17.1 Prevalence sub-study

Prevalence of asymptomatic carriage of C. diff and justification

A stool sample will be taken from all consenting service users during a one week collection phase in each of the nine care homes. Antibiotic use data for the previous three months will also be collected from the service users care notes. Service users will be welcome to participate in the remainder of the observational study if they decline to participate in this prevalence sub-study. This prevalence sub-study of asymptomatic carriage of *C. diff* will help establish the magnitude of the problem. CDAD usually occurs in the face of asymptomatic infection, cross

contamination and antibiotic use. Knowing the prevalence of asymptomatic infection and the variation between care homes will therefore inform an appraisal of the seriousness and potential seriousness of the problem, including considering cycling asymptomatic and symptomatic infection between care homes and hospitals. Stool samples will be taken by concentrating a resource in each care home for a single week, as close to the beginning of the study as possible, so that they are supported in recruitment and sampling by a study researcher.

C. diff carriage rates are important to us for the following reasons:

1. We know neither the carriage rate in UK nursing/care homes, nor the variability in carriage between homes, and between different sizes and types of homes. Existing data is old, often derived in outbreak conditions, and obtained in the US and therefore not applicable to the UK, where antibiotic prescribing, organisation of care, and prevalent strains of *C. diff* (e.g. 027) are all different.

2. The risk of a service user developing *C. diff*-associated diarrhoea is greatly affected by the prevalence of *C. diff* colonisation in the home. Service users could be:

a. Colonised with C. diff

b. Not colonised with *C. diff*, but in a home with a high prevalence of *C. difficile* colonisation and therefore with a high likelihood of coming into contact with *C. diff* during antibiotic therapy.

c. Not colonised with *C. diff*, and in a home with no one colonised with *C. diff* and, therefore, at very low risk of contacting it during antibiotic therapy.

If probiotics mainly protect against CDAD rather than other forms of AAD, there is a danger of a type II error if we recruit from homes where service users are mainly in group (c). If probiotics protected against AAD other than CDAD, we would wish to include all care homes in Stage 2. A potentially useful finding could be that probiotics are a useful intervention in homes with a high rate of *C. diff* colonisation (which might be easily predicted by size/nursing dependence etc., data that we will collect in Stage 1 and subject to exploratory analyses of this type).

When the baseline stool sample is collected we will also examine the service users care notes for information about any antibiotics prescribed in the last three

PAAD Study: Establishing the platform. Version 7.0, dated 17/08/2011 38

months. This will provide valuable information for comparing to the antimicrobial sensitivities of bacterial isolates identified in baseline stool samples.

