2.1.4 CDAD and AAD infection in care homes

There is limited data regarding antibiotic use, and incidence of AAD and CDAD in care homes. Most of the research to date has been carried out in hospital settings or in the US. However, residents in care homes in the UK have many of the risk factors associated with developing AAD and CDAD (e.g. over 65 years, frail, multiple co-morbidities).

Antibiotic use in US residential homes is common: estimations of single timepoint prevalence ranges from 8% to 17%. Between 50% to 75% of residents received at least one antibiotic prescription over a twelve-month period [8]. We conducted a prescribing audit of care homes in one Health Authority and found that 134 (7%) of 1901 residents were on an antibiotic on a single day. A study in care homes in Sweden showed 25% of service users were prescribed an antibiotic during a three month observation period.[12] Considerably fewer antibiotics are prescribed in Sweden compared to the UK.[13] We do not know how many of these service users developed AAD nor how many had *C. difficile*. Providing reasonable estimates of these outcomes for the UK relate to the scientific importance of our study to the NHS. Diarrhoea within long term care facilities can cause fatalities and may become endemic. Up to 33% of patients in secondary care in the UK develop diarrhoea after antibiotic treatment.

Laffan and colleagues retrospectively reviewed CDAD incidence and prevalence in a single 200 bed Long Term Care Facility (LTCF) in Baltimore in the US between July 2001 and December 2003. Incidence of CDAD ranged form 0 to 2.62 cases per 1000 resident days. They found that CDAD in this LTCF occurred most often in patients who had recently been admitted to hospital [14]. US studies by Kutty and colleagues and Chang and colleagues found that over 90% of post hospitalisation cases of CDAD occur within 30 days of discharge [15, 16] Riggs and colleagues in the US found that over 50% of patients admitted to a LTCF during an outbreak were asymptomatic carriers of *C.difficile* (stool culture positive but no diarrhoea) [17].

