3.2 Secondary objectives and sub-study objectives

Observational study

1) To conduct prospective systematic ascertainment of antibiotic use in care homes

2) To estimate the risk of AAD overall and from particular antibiotics in care home settings;

3) To identify barriers and implementation issues in conducting a trial of AAD prevention/amelioration in a care home setting.

Sub Study 1. Prevalence:

1) To determine the prevalence of asymptomatic *C. difficile* carriage in service users within selected care homes.

Sub Study 2 Qualitative Observational Study of Care Home Routines

- To better understand the range of daily care culture and schedules within care home settings (including delivery of food and drink, communication, skill mix, administration, visiting arrangements, toileting arrangements etc).
- To determine what level of assistance the care home staff require to deliver the study
- 3) To assess the level of data we can feasibly collect
- To assess the best method and timing of drug delivery and administration of probiotic/placebo
- 5) To determine whether study procedures are likely to be effectively communicated throughout the home.

Sub study 3. Qualitative:

 To conduct focus groups and individual qualitative interviews with service users, their family, care home staff and General Practitioners. To explore the ethical and practical issues of consent and assent, particularly the topic of advanced consent, for elderly residents who may/may not have capacity to consent

Sub study 4 - EQ-5D By Proxy

1) This sub- study is testing the hypothesis that there is an inverse relationship between agreement in subject/proxy EQ-5D scores and the

subject's level of cognitive competence. If results support this hypothesis, then a minimum level of cognitive competence will be identified below which EQ-5D data should be collected by proxy.

2) The study will also explore whether a combination of professional and friend/relative proxies would be preferable to either proxy alone.

4 Study design

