Stage 1 of PAAD is a prospective observational study that will collect initial data (e.g. amount and type of antibiotics used, episodes of AAD and CDAD and outcome) for 12 months on 270 service users in a purposive sample of nine care homes in South Wales. This will identify the scale of the problem, provide incidence data to determine whether the trial (Stage 2) is justified, and if so, provide the basis of our sample size calculation. Certain research procedures for the RCT (Stage 2) will also be piloted and developed within Stage 1.

Within the first Stage there will be three sub studies imbedded within the main study (see section 17 for more details). These are:

1) Prevalence Sub Study:

To establish the asymptomatic carriage of *C. diff* in care home service users in each care home. This will occur during a one-week collection phase in each of the included care homes. This is an optional component for all service users.

Antibiotic prescribing data for the previous three months for each of the service users taking part in this sub study will also be collected. This will provide valuable research information for comparing to the antimicrobial sensitivities of bacterial isolates identified in baseline stool samples.

2) Sub Study 2 Qualitative Observational Study of Care Home Routines

PAAD sub-study 2 is a qualitative observation study which we aim to conduct in 5 of the 10 care homes participating in PAAD stage 1. Care home staff will be informed that a researcher is observing daily care routines. Service users and relatives will not be informed that a researcher is observing daily care routines.

Sub-study 2 is being conducted as a pre-research study (ie. to inform the design of PAAD stage 2) and not a research study.

3) Qualitative Sub Study:

To establish the feasibility and acceptability of taking advance consent/assent for research trial procedures in care home service users. This will be achieved through conduction of 18 focus groups with family members and care staff, and qualitative interviews with GPs and service users at nine homes.

4) EQ-5D by Proxy

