6.2 Exclusion criteria

There are no exclusion criteria for the PAAD Observational Study.

7 Recruitment

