- 4. Where service users have capacity, the service user will sign and date the consent form, with the trained senior care home staff / nursing staff or research nurse taking consent. If the service user consents and agrees, then the service user's representative will be informed that the service user is taking part in the study, and will be sent information about the study.
- 5. Where service users lack capacity, the service user's representative (consultee) will be provided with information about the study and will be asked for advice about whether or not the service user would want to join the study. The representative will be asked to provide assent for the service user to join the study.
- If no next of kin or representative can be contacted we will, as suggested by the 2005 Mental Capacity Act s32(3), nominate an appropriate person, e.g. Age Concern Advocate or GP, to give advice. (http://www.opsi.gov.uk/acts/acts2005/20050009.htm).

The following information sheets will be provided to the care homes:

Service user

- 1) Summary service user information sheet
- 2) Pictorial service user information sheet
- 3) Detailed service user information sheet
- 4) Service user consent form

Service user's representative

PAAD Study: Establishing the platform. Version 7.0 , dated 17/08/2011 23

- 1) Detailed consultee information sheet
- 2) Consultee consent form

We will repeat this process for any new permanent resident moving into participating care homes up to five months following recruitment start in that care home.

The service user / representative must personally sign and date the latest approved version of the informed consent form before any study specific procedures are performed.

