8.5 Microbiology and Stool sample collection (baseline prevalence stool and loose stool)

A standardised protocol on when and how to take a stool sample will be provided.

Baseline prevalence stool sample:

The baseline prevalence stool samples will be collected by a care home staff / study research nurse and should be collected within one week of consent. The sample will be put into containers provided by the study team, which are recommended by the Microbiology laboratory. This container will be labelled with the participants ID number, initials and date of birth and sent by 1^{st} Class Royal Mail using Post Office approved SafeboxesTM, a method that meets legal requirements. The sample will be sent to the Public Health Wales Microbiology laboratory for *C. difficile* culture and storage at -70°C. Any cultured *C. diff* isolates will be ribo-typed, toxin tested, and have antimicrobial sensitivity testing done, as well as screening for carriage of antibiotic resistant bacteria. Results on baseline samples are for research purposes only and will not be sent back to care homes or GPs. The research team will receive results of study diagnostic stool sample analyses.

Loose Stool sample:

Diagnostic samples (DS) from service users who develop AAD will be sent, as per routine procedure, to local laboratories for routine analysis to include testing for the presence of *C.difficile* toxins A and B, and results will be sent back to the GP, who will subsequently notify the care home of the result. Another sample will be sent, along with the appropriate stool CRF, to central reference laboratory for *C.difficile* culture as above and as well as screening for carriage of antibiotic resistant bacteria. The results of study diagnostic stool sample analyses will be sent to the SEWTU. Expert guidance and support will be given to the care home staff and the GP on how to manage positive results.

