12.2 Sub-Study analysis

Sub-Study 1. Prevalence:

1. To determine the prevalence of asymptomatic carriage of *C. difficile*.

Sub-Study 2. Qualitative Observational Study of Care Home Routines :

Data gathered on the observation schedule will be collated, entered onto a spreadsheet for ease of comparison, and discussed between the 3 observers. Any inconsistencies will be debated and, if necessary, resolved by a further visit. A short report on the daily care routines will be prepared for each home and sent to the matron for validation. Feedback from this validation process will be incorporated into a final report on the daily care routines of the PAAD care homes which will then be used to inform the design of PAAD stage 2.

Sub-Study 3. Qualitative sub study

Data will be analysed using Framework Analysis. This approach involves the following steps: familiarisation, creating a thematic framework, indexing, charting, mapping and interpretation. The thematic framework will be developed iteratively, informed by the data and agreed during study team meetings. NVivo 8 software will be used for the indexing stage. A proportion (20%) of transcripts will be double coded by more than one researcher. Disagreements about coding will be resolved, where necessary, in a series of study group meetings.

Sub-Study 4. EQ-5D Sub Study

Given the relatively small sample and the exploratory nature of this sub-study, the results will be used to generate hypotheses rather than test them. Agreement in overall EQ-5D scores between proxies and the SU will be assessed using the Bland/Altman method to estimate 95% limits of agreement.

As data on the individual EQ-5D dimensions are trichotomous (score = 1, 2 or 3) we will use a Kappa statistic to examine agreement between scores obtained from a relative and carer for both SU/proxy on each dimension.

We will also use a Kappa statistic to examine agreement between the carer, research nurse and SU's assessment of the SUs cognitive ability on the day and, via ANOVA, will explore differences between the average MMSE scores and those who said 'yes' or 'no' regarding the SU's level of cognitive ability.

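### Sub-study 1 targets asymptomatic *C. difficile* carriage but sets no symptom condition at sampling and gives two sampling times, so its figure can include residents with diarrhoea and mix point prevalence with carriage on entry

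*Protocol*

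**What the plan says.** **Target.** Protocol section 3.2 sets the objective: "To determine the prevalence of asymptomatic *C. difficile* carriage in service users within selected care homes". Sections 4, 11.2, 12.2 and 17.1 also speak of asymptomatic carriage or carriers. The summary in section 1.1 drops the qualifier and speaks only of *C. difficile* prevalence. The only gloss of an asymptomatic carrier is in section 2.1.4, where a US study is cited: "stool culture positive but no diarrhoea".

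**Who is sampled.** Section 17.1: "A stool sample will be taken from all consenting service users during a one week collection phase in each of the nine care homes". Section 6.2 adds: "There are no exclusion criteria for the PAAD Observational Study".

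**When.** Section 4 says of the sub-study: "This will occur during a one-week collection phase in each of the included care homes". Section 17.1 agrees and places that week as near the study start as possible. Section 8.5, however, says the baseline sample "should be collected within one week of consent", and Table 1 gives the same timing for the Prevalence Study Stool CRF.

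**How long residents can enter.** Section 7.2 repeats the consent process for "any new permanent resident moving into participating care homes up to five months following recruitment start in that care home". Section 7.1 allows recruitment to continue until three months before the study ends, to make up for losses.

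**Use of the result.** Section 10.1 lists asymptomatic carriage under sample size calculation. Section 11.2 says the early evaluation will give the number of asymptomatic carriers and that these data will help justify Stage 2. Section 17.1 wants the variation between homes.

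**The concern.** The population sampled is wider than the population named in the objective. A resident who has diarrhoea when sampled and whose culture is positive is not an asymptomatic carrier, yet nothing shown keeps that result out of the estimate. Daily Bristol typing (section 8.3 and Table 1) starts only when an antibiotic is prescribed, so it does not routinely describe stool form at the baseline sample.

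The two timing rules also define different quantities. One week per home gives a point prevalence among the residents then present. Sampling within a week of each consent adds residents who arrive over later months, and for them the result is carriage on entry. Staff handling a later entrant cannot tell from the protocol whether a prevalence sample is due.

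At stake is a figure that feeds the Stage 2 sample size work and the case for proceeding. Comparing homes also needs the same sampling window in each. An analysis plan cannot repair this alone: if stool form is not captured at sampling, it must be recovered from other records.

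**Working it through.** **1. No stated figure to reproduce.** The protocol gives no expected prevalence, sample size or precision for sub-study 1. The checks below size the two defects.

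**2. Timing rules side by side.**

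| Rule | Source | Sampling span within a home |
|---|---|---|
| Single collection week | Sections 4, 17.1 | 1 week |
| Within a week of consent, entry to 5 months | Table 1, 8.5 with 7.2 | About 5 months |
| Within a week of consent, entry to 3 months before the end | Table 1, 8.5 with 7.1 | 12 − 3 = about 9 months |

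The first rule matches the others only for residents who consent around the collection week. The early evaluation in section 11.2 uses 3 + 2 = 5 months of data. Under the nine-month reading, prevalence samples would still be arriving after it.

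**3. Size of the symptom mixing.** Let s be the share of residents with diarrhoea when sampled, c0 the carriage among those without diarrhoea, and c1 the positivity among those with diarrhoea.

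- Observed proportion = (1 − s) × c0 + s × c1
- Excess over c0 = s × (c1 − c0)

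Inputs: s = 2–10% and c0 = 2–10% are assumptions, since the protocol gives neither. For c1, 20–30% is borrowed from section 2.1.3, which gives it as the share of AAD due to *C. difficile*. Using it as culture positivity in residents with diarrhoea is a further assumption.

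- Smallest: s = 2%, c0 = 10%, c1 = 20%: 0.02 × 0.10 = 0.002, or 0.2 points.
- Middle: s = 5%, c0 = 5%, c1 = 20–30%: 0.05 × 0.15 = 0.0075 to 0.05 × 0.25 = 0.0125. The observed figure is 5.75–6.25% instead of 5%.
- Largest: s = 10%, c0 = 2%, c1 = 30%: 0.10 × 0.28 = 0.028, or 2.8 points.

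**4. Comparison with sampling error.** The 95% half-width is 1.96 × √(p(1 − p)/n), with n = 270 pooled and 270/9 = 30 per home (section 11.1).

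| Carriage c0 | Excess from mixing (points) | Half-width, n = 270 | Half-width, n = 30 |
|---|---|---|---|
| 2% | 0.4–2.8 | ±1.7 | ±5.0 |
| 5% | 0.3–2.5 | ±2.6 | ±7.8 |
| 10% | 0.2–2.0 | ±3.6 | ±10.7 |

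These half-widths assume full uptake of an optional sub-study and ignore clustering by home, so the real ones would probably be wider. At n = 30 and low carriage the normal approximation is only a rough yardstick.

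In the pooled estimate the excess can approach the half-width, and at 2% carriage can exceed it. Within a home, sampling error is clearly larger.

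**5. What limits home-level reading.** The chance of no positive among 30 is (1 − p)^30: 54.5%, 21.5% and 4.2% at carriage of 2%, 5% and 10%. With 0 of 30 positive, the 97.5% upper bound is 1 − 0.025^(1/30) = 11.6%.

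**The case against.** **Timing.** Section 7.2 aims to recruit everyone at the outset, section 8 takes sub-study consent at initial recruitment, and section 17.1 supports recruitment and sampling together in one week. For those residents the two rules coincide. The nine-month span is a worst case from a clause about the main-study target of 270, and nothing says that late replacements give a prevalence sample. This narrows the conflict but does not remove it. Section 7.2 takes new residents through the same process for five months, and Table 1 and section 8.5 contain no exception for them.

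**Stool form.** Section 8.5 promises a standardised sampling procedure, and Table 1 lists a Prevalence Study Stool CRF and a Loose Stool CRF. None is shown, so it cannot be said that stool form goes unrecorded. Restricting numerator and denominator could also be left to an analysis plan. That stands, but the protocol text does not require the information at the baseline sample, and the analysis depends on having it.

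**Stronger readings.** A reader might infer that the figure cannot classify homes, or that a positive resident with diarrhoea wrongly moves a home from group (c) to group (b) in section 17.1. The documents do not support this. Those groups rest on any colonisation in the home, and a positive resident with diarrhoea is colonised, so counting that resident there is correct. A colonised newcomer is likewise a possible source of contact. One positive in 30 is 3.3 points, but it is a real positive, and the small number per home limits classification more.

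A reader might also infer that the figure mixes seasons. Section 2.1.1 states seasonality for AAD, not for carriage, and a spread over months arises only under the consent-based rule.

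**Conclusion.** Two defects hold. The target is asymptomatic carriage, but all consenting residents are sampled with no stated condition on, or recording of, diarrhoea. The two sampling times disagree for later entrants, so point prevalence can be mixed with carriage on entry.

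The symptom mixing is modest: about 0.2–2.8 points in the pooled figure, against a pooled half-width of about 1.7–3.6 points. It rests on the assumed ranges for diarrhoea and carriage and on the borrowed 20–30% positivity. The timing effect cannot be sized, because the protocol gives neither the number of later entrants nor their carriage.

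The conclusion goes no further. It concerns the asymptomatic carriage estimate and its use in sections 10.1 and 11.2. It does not show that homes cannot be grouped, that symptomatic positives misplace them, or that carriage differs by season. Because the figure informs the Stage 2 decision and the repair is cheap, the protocol should be corrected.

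**What to change.** - **One sampling rule.** In Table 1, section 8.5 and section 17.1, state that point prevalence uses residents sampled in the home's collection week. Report any samples from later entrants separately as carriage on entry.
- **Record symptoms.** Have the Prevalence Study Stool CRF record stool form or diarrhoea at sampling, if it does not already. For samples already taken, extract this from care home records where consent covers it (section 8.6).
- **Two reported figures.** In section 12.2, report asymptomatic carriage with numerator and denominator limited to residents without diarrhoea. Report overall colonisation, including residents with diarrhoea, separately, and use that figure for groups (a)–(c) in section 17.1. Using the restricted figure there could label a home uncolonised when its only positive resident has diarrhoea.
- **Wording.** Align section 1.1 with the chosen target.

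The cost is protocol wording, one or two CRF items and possibly some record extraction, with no extra samples. The drawback is a slightly smaller denominator for the asymptomatic point prevalence.
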